Appendix 5: ACQ-7

For illustrative purposes only:

ASTHMA CONTROL QUESTIONNAIRE®		PATIENT ID: _____
		DATE: _____
Page 1 of 2		
Please answer questions 1 - 6.		
Circle the number of the response that best describes how you have been during the past week.		
1. On average, during the past week, how often were you woken by your asthma during the night?	0 Never 1 Hardly ever 2 A few times 3 Several times 4 Many times 5 A great many times 6 Unable to sleep because of asthma	
2. On average, during the past week, how bad were your asthma symptoms when you woke up in the morning?	0 No symptoms 1 Very mild symptoms 2 Mild symptoms 3 Moderate symptoms 4 Quite severe symptoms 5 Severe symptoms 6 Very severe symptoms	
3. In general, during the past week, how limited were you in your activities because of your asthma?	0 Not limited at all 1 Very slightly limited 2 Slightly limited 3 Moderately limited 4 Very limited 5 Extremely limited 6 Totally limited	
4. In general, during the past week, how much shortness of breath did you experience because of your asthma?	0 None 1 A very little 2 A little 3 A moderate amount 4 Quite a lot 5 A great deal 6 A very great deal	

ASTHMA CONTROL QUESTIONNAIRE®		PATIENT ID: _____
		DATE: _____
Page 2 of 2		
5. In general, during the past week, how much of the time did you wheeze?	0 Not at all 1 Hardly any of the time 2 A little of the time 3 A moderate amount of the time 4 A lot of the time 5 Most of the time 6 All the time	
6. On average, during the past week, how many puffs/inhalations of short-acting bronchodilator (e.g. Ventolin/Bricanyl) have you used each day? (If you are not sure how to answer this question, please ask for help)	0 None 1 1 - 2 puffs/inhalations most days 2 3 - 4 puffs/inhalations most days 3 5 - 8 puffs/inhalations most days 4 9 - 12 puffs/inhalations most days 5 13 - 16 puffs/inhalations most days 6 More than 16 puffs/inhalations most days	
To be completed by a member of the clinic staff		
7. FEV ₁ pre-bronchodilator:	0 > 95% predicted 1 95 - 90% 2 89 - 80% 3 79 - 70% 4 69 - 60% 5 59 - 50% 6 < 50% predicted	
FEV ₁ predicted:.....		
FEV ₁ % predicted:..... (Record actual values on the dotted lines and score the FEV₁% predicted in the next column)		

Appendix 6: AQLQ-S +12

For illustrative purposes only:

ASTHMA QUALITY OF LIFE QUESTIONNAIRE (S)	PATIENT ID: _____																																																																
SELF-ADMINISTERED	DATE: _____																																																																
Page 1 of 5																																																																	

Please complete all questions by circling the number that best describes how you have been during the last 2 weeks as a result of your asthma.
 
HOW LIMITED HAVE YOU BEEN DURING THE LAST 2 WEEKS IN THESE ACTIVITIES AS A RESULT OF YOUR ASTHMA?
 
  
 	Totally Limited	Extremely Limited	Very Limited	Moderate Limitation	Some Limitation	A Little Limitation	Not at all Limited	
   
 1. STRENUOUS ACTIVITIES (such as hurrying, exercising, running up stairs, sports)	1	2	3	4	5	6	7	
 
 2. MODERATE ACTIVITIES (such as walking, housework, gardening, shopping, climbing stairs)	1	2	3	4	5	6	7	
 
 3. SOCIAL ACTIVITIES (such as talking, playing with pets/children, visiting friends/relatives)	1	2	3	4	5	6	7	
 
 4. WORK/SCHOOL-RELATED ACTIVITIES* (tasks you have to do at work/in school)	1	2	3	4	5	6	7	
 
 5. SLEEPING	1	2	3	4	5	6	7	
  
 
*If you are not employed or self-employed, these should be tasks you have to do most days.
 
HOW MUCH DISCOMFORT OR DISTRESS HAVE YOU FELT DURING THE LAST 2 WEEKS?
 
  
 	A Very Great Deal	A Great Deal	A Good Deal	Moderate Amount	Some	Very Little	None	
   
 6. How much discomfort or distress have you felt over the last 2 weeks as a result of CHEST TIGHTNESS?	1	2	3	4	5	6	7	
  
			Totally Limited	Extremely Limited	Very Limited	Moderate Limitation	Some Limitation	A Little Limitation	Not at all Limited	1. STRENUOUS ACTIVITIES (such as hurrying, exercising, running up stairs, sports)	1	2	3	4	5	6	7	2. MODERATE ACTIVITIES (such as walking, housework, gardening, shopping, climbing stairs)	1	2	3	4	5	6	7	3. SOCIAL ACTIVITIES (such as talking, playing with pets/children, visiting friends/relatives)	1	2	3	4	5	6	7	4. WORK/SCHOOL-RELATED ACTIVITIES* (tasks you have to do at work/in school)	1	2	3	4	5	6	7	5. SLEEPING	1	2	3	4	5	6	7		A Very Great Deal	A Great Deal	A Good Deal	Moderate Amount	Some	Very Little	None	6. How much discomfort or distress have you felt over the last 2 weeks as a result of CHEST TIGHTNESS?	1	2	3	4	5	6	7
	Totally Limited	Extremely Limited	Very Limited	Moderate Limitation	Some Limitation	A Little Limitation	Not at all Limited																																																										
1. STRENUOUS ACTIVITIES (such as hurrying, exercising, running up stairs, sports)	1	2	3	4	5	6	7																																																										
2. MODERATE ACTIVITIES (such as walking, housework, gardening, shopping, climbing stairs)	1	2	3	4	5	6	7																																																										
3. SOCIAL ACTIVITIES (such as talking, playing with pets/children, visiting friends/relatives)	1	2	3	4	5	6	7																																																										
4. WORK/SCHOOL-RELATED ACTIVITIES* (tasks you have to do at work/in school)	1	2	3	4	5	6	7																																																										
5. SLEEPING	1	2	3	4	5	6	7																																																										
	A Very Great Deal	A Great Deal	A Good Deal	Moderate Amount	Some	Very Little	None																																																										
6. How much discomfort or distress have you felt over the last 2 weeks as a result of CHEST TIGHTNESS?	1	2	3	4	5	6	7																																																										

ASTHMA QUALITY OF LIFE QUESTIONNAIRE (S)

PATIENT ID: _____

SELF-ADMINISTERED

DATE: _____

Page 2 of 5

IN GENERAL, HOW MUCH OF THE TIME DURING THE LAST 2 WEEKS DID YOU:

	All of the Time	Most of the Time	A Good Bit of the Time	Some of the Time	A Little of the Time	Hardly Any of the Time	None of the Time
7. Feel CONCERNED ABOUT HAVING ASTHMA?	1	2	3	4	5	6	7
8. Feel SHORT OF BREATH as a result of your asthma?	1	2	3	4	5	6	7
9. Experience asthma symptoms as a RESULT OF BEING EXPOSED TO CIGARETTE SMOKE?	1	2	3	4	5	6	7
10. Experience a WHEEZE in your chest?	1	2	3	4	5	6	7
11. Feel you had to AVOID A SITUATION OR ENVIRONMENT BECAUSE OF CIGARETTE SMOKE?	1	2	3	4	5	6	7

HOW MUCH DISCOMFORT OR DISTRESS HAVE YOU FELT DURING THE LAST 2 WEEKS?

	A Very Great Deal	A Great Deal	A Good Deal	Modest Amount	Some	Very Little	None
12. How much discomfort or distress have you felt over the last 2 weeks as a result of COUGHING?	1	2	3	4	5	6	7

IN GENERAL, HOW MUCH OF THE TIME DURING THE LAST 2 WEEKS DID YOU:

	All of the Time	Most of the Time	A Good Bit of the Time	Some of the Time	A Little of the Time	Hardly Any of the Time	None of the Time
13. Feel FRUSTRATED as a result of your asthma?	1	2	3	4	5	6	7
14. Experience a feeling of CHEST HEAVINESS?	1	2	3	4	5	6	7

ASTHMA QUALITY OF LIFE QUESTIONNAIRE (S)		PATIENT ID: _____					
SELF-ADMINISTERED		DATE: _____					
Page 3 of 5							
IN GENERAL, HOW MUCH OF THE TIME DURING THE LAST 2 WEEKS DID YOU:							
	All of the Time	Most of the Time	A Good Bit of the Time	Some of the Time	A Little of the Time	Hardly Any of the Time	None of the Time
15. Feel CONCERNED ABOUT THE NEED TO USE MEDICATION for your asthma?	1	2	3	4	5	6	7
16. Feel the need to CLEAR YOUR THROAT?	1	2	3	4	5	6	7
17. Experience asthma symptoms as a RESULT OF BEING EXPOSED TO DUST?	1	2	3	4	5	6	7
18. Experience DIFFICULTY BREATHING OUT as a result of your asthma?	1	2	3	4	5	6	7
19. Feel you had to AVOID A SITUATION OR ENVIRONMENT BECAUSE OF DUST?	1	2	3	4	5	6	7
20. WAKE UP IN THE MORNING WITH ASTHMA SYMPTOMS?	1	2	3	4	5	6	7
21. Feel AFRAID OF NOT HAVING YOUR ASTHMA MEDICATION AVAILABLE?	1	2	3	4	5	6	7
22. Feel bothered by HEAVY BREATHING?	1	2	3	4	5	6	7
23. Experience asthma symptoms as a RESULT OF THE WEATHER OR AIR POLLUTION OUTSIDE?	1	2	3	4	5	6	7
24. Were you WOKEN AT NIGHT by your asthma?	1	2	3	4	5	6	7
25. AVOID OR LIMIT GOING OUTSIDE BECAUSE OF THE WEATHER OR AIR POLLUTION?	1	2	3	4	5	6	7

ASTHMA QUALITY OF LIFE QUESTIONNAIRE (S)		PATIENT ID: _____					
SELF-ADMINISTERED		DATE: _____					
Page 4 of 5							
IN GENERAL, HOW MUCH OF THE TIME DURING THE LAST 2 WEEKS DID YOU:							
	All of the Time	Most of the Time	A Good Bit of the Time	Some of the Time	A Little of the Time	Hardly Any of the Time	None of the Time
26. Experience asthma symptoms as a RESULT OF BEING EXPOSED TO STRONG SMELLS OR PERFUME?	1	2	3	4	5	6	7
27. Feel AFRAID OF GETTING OUT OF BREATH?	1	2	3	4	5	6	7
28. Feel you had to AVOID A SITUATION OR ENVIRONMENT BECAUSE OF STRONG SMELLS OR PERFUME?	1	2	3	4	5	6	7
29. Has your asthma INTERFERED WITH GETTING A GOOD NIGHT'S SLEEP?	1	2	3	4	5	6	7
30. Have a feeling of FIGHTING FOR AIR?	1	2	3	4	5	6	7
HOW LIMITED HAVE YOU BEEN DURING THE LAST 2 WEEKS?							
	Severely Limited Most Not Done	Very Limited	Moderately Limited Several Not Done	Slightly Limited	Very Slightly Limited Very Few Not Done	Hardly Limited At All	Not Limited Have Done All Activities
31. Think of the OVERALL RANGE OF ACTIVITIES that you would have liked to have done during the last 2 weeks. How much has your range of activities been limited by your asthma?	1	2	3	4	5	6	7

ASTHMA QUALITY OF LIFE QUESTIONNAIRE(S)

PATIENT ID: _____

SELF-ADMINISTERED

DATE: _____

[figure not shown]
Page 5 of 5

[figure not shown]
HOW LIMITED HAVE YOU BEEN DURING THE LAST 2 WEEKS?

[figure not shown]
	Totally Limited	Extremely Limited	Very Limited	Moderate Limitation	Some Limitation	A Little Limitation	Not at all Limited
32. Overall, among ALL THE ACTIVITIES that you have done during the last 2 weeks, how limited have you been by your asthma?	1	2	3	4	5	6	7

DOMAIN CODE:

Symptom: 6, 8, 10, 12, 14, 16, 18, 20, 22, 24, 25, 30
Activity Limitation: 1, 2, 3, 4, 5, 11, 19, 25, 28, 31, 32
Emotional Function: 7, 13, 15, 21, 27
Environmental Stimuli: 9, 17, 23, 26

Appendix 8: Patient Asthma Control e-Diary

For illustrative purposes only:

The following information will be captured:

In the MORNING	In the EVENING
Peak expiratory flow rate	
How did you sleep last night ?	
Did you have asthma symptoms upon awakening in the morning?	
Number of puffs of rescue medication during the past 12 hours	
	Peak expiratory flow rate
	Did your respiratory symptoms stop you from performing your usual daily activities?
	How severe was your shortness of breath today?
	How was your wheeze during the past 12 hours?
	How was your cough during the past 12 hours?
	Did you have Chest tightness during the past 12 hours?
	Number of puffs of rescue medication during the past 12 hours

Appendix 9: Liver event definitions and follow-up requirements

Table 13-1 Liver Event Definitions

	Definition/ threshold
Adverse event of special interest	
Laboratory values	ALT or AST > 3 x ULN ALP > 2 x ULN TBL > 1.5 x ULN
Medically significant event (SAE)	
Laboratory values	ALT or AST > 5 x ULN (with or without TBL > 2 x ULN [mainly conjugated fraction]) ALP > 5 x ULN (with or without TBL > 2 x ULN [mainly conjugated fraction]) TBL > 3 x ULN Potential Hy's Law cases (defined as ALT/AST > 3 x ULN and TBL > 2 x ULN [mainly conjugated fraction] without notable increase in ALP to > 2 x ULN)
Adverse events	Any clinical event of jaundice (or equivalent term) ALT or AST > 3 x ULN accompanied by general malaise, fatigue, abdominal pain, nausea, or vomiting, or rash with eosinophilia Any event that links to a preferred term (PT) in the MedDRA dictionary falling under the SMQ sub-module "Drug-related hepatic disorders – severe events only"* or any "Hy's law case" PT

* These events cover the following: hepatic failure, fibrosis and cirrhosis, and other liver damage-related conditions; the non-infectious hepatitis; the benign, malignant and unspecified liver neoplasms

Table 13-2 Liver Event Follow Up Requirements

[figure not shown]
[figure not shown]
Criteria	Event type	Actions required	Follow-up monitoring
Potential Hy's Law case ^a	Medically significant	Discontinue the study drug immediately Hospitalize, if clinically appropriate Report to Novartis as an SAE Establish causality	ALT, AST, TBL, Alb, PT, ALP and γ GT until resolution ^c (frequency at investigator discretion)
ALT or AST			
> 8 x ULN	Medically significant	Repeat LFT within 48 hours If elevation persists, discontinue the study drug immediately Hospitalize if clinically appropriate Report to Novartis as an SAE Establish causality	ALT, AST, TBL, Alb, PT, ALP and γ GT until resolution ^c (frequency at investigator discretion)
> 5 to \leq 8 x ULN	Medically significant	Repeat LFT within 48 hours If elevation persists for more than 2 weeks , discontinue the study drug Report to Novartis as an SAE Establish causality	ALT, AST, TBL, Alb, PT, ALP and γ GT until resolution ^c (frequency at investigator discretion)
> 3 x ULN accompanied by symptoms ^b	Medically significant	Discontinue the study drug immediately Hospitalize if clinically appropriate Report to Novartis as an SAE Establish causality	ALT, AST, TBL, Alb, PT, ALP and γ GT until resolution ^c (frequency at investigator discretion)
> 3 to \leq 5 x ULN (patient is asymptomatic)	AESI	Central laboratory to report to Investigator & Novartis Repeat LFT once or twice in the week If elevation persists, establish causality	Investigator discretion Monitor LFT within 1 to 4 weeks or at next visit
\leq 3 x ULN (patient is asymptomatic)	N/A	Repeat LFT at next visit	
ALP (isolated)			
> 5 x ULN	Medically significant	Repeat LFT within 48 hours If elevation persists, report to Novartis as an SAE Establish causality	Investigator discretion Monitor LFT within 1 to 4 weeks or at next visit
> 2 to \leq 5 x ULN (patient is asymptomatic)	AESI	Central laboratory to report to Investigator & Novartis Repeat LFT once or twice in the week If elevation persists, establish causality	Investigator discretion Monitor LFT within 1 to 4 weeks or at next visit
\leq 2 x ULN	N/A	Repeat LFT at next visit	

[figure not shown]
Criteria	Event type	Actions required	Follow-up monitoring
(patient is asymptomatic)			
TBL (isolated)			
> 3 x ULN	Medically significant	Repeat LFT within 48 hours If elevation persists, discontinue the study drug immediately Hospitalize if clinically appropriate Report to Novartis as an SAE Establish causality	ALT, AST, TBL, Alb, PT, ALP and γ GT until resolution ^c (frequency at investigator discretion) Test for hemolysis (e.g., reticulocytes, haptoglobin, unconjugated [indirect] bilirubin)
> 1.5 to \leq 3 x ULN (patient is asymptomatic)	AESI	Central laboratory to report to Novartis Repeat LFT once or twice in the week if elevation persists, establish causality	investigator discretion Monitor LFT within 1 to 4 weeks or at next visit
\leq 1.5 x ULN (patient is asymptomatic)	N/A	Repeat LFT at next visit	
Preferred terms			
Jaundice	Medically significant	Discontinue the study drug immediately Hospitalize the patient Report to Novartis as an SAE Establish causality	ALT, AST, TBL, Alb, PT, ALP and γ GT until resolution ^c (frequency at investigator discretion)
"Drug-related hepatic disorders - severe events only" SMQ AE	Medically significant	Discontinue the study drug hospitalization if clinically appropriate Report to Novartis as an SAE Establish causality	Investigator discretion

^a Elevated ALT/AST > 3 x ULN and TBL > 2 x ULN but with no notable increase in ALP to > 2 x ULN

^b General malaise, fatigue, abdominal pain, nausea, or vomiting, rash with eosinophilia

^c Resolution is defined as an outcome of one of the following: return to baseline values, stable values at three subsequent monitoring visits at least 2 weeks apart, remain at elevated level after a maximum of 6 months, liver transplantation, and death.

Appendix 11: ICS Dose level

Table 13-3 Low, medium and high Daily Doses of Inhaled Glucocorticosteroids for Adults and adolescents (12 years and older)* (GINA 2015)

Drug	Total Daily Dose (µg/day)		
	Low	Medium	High
Beclomethasone dipropionate – CFC*	200-500	> 500 – 1000	> 1000
Beclomethasone dipropionate – HFA	100-200	> 200 – 400	> 400
Budesonide- DPI	200-400	> 400 – 800	> 800
Ciclesonide – HFA	80-160	> 160 – 320	> 320
Fluticasone propionate – DPI	100-250	> 250 – 500	> 500
Fluticasone propionate – HFA	100-250	> 250 – 500	> 500
Fluticasone Furoate**	NA	100	200
Mometasone furoate	110-220	> 220-440	≥ 440
Triamcinolone acetonide	400-1000	> 1000 – 2000	> 2000

DPI: dry powder inhaler; HFA: hydrofluoroalkane propellant.

* Beclomethasone dipropionate CHF is included for comparison with older literature.

** As per SmPC

Appendix 12: Estimation of non-inferiority margin of comparing QMF149 versus active control (salmeterol xinafoate /fluticasone propionate)

The non-inferiority margin of QMF149 vs active control (salmeterol xinafoate /fluticasone propionate) is based on the results from Kavuru et al (2000), Nathan et al (2006), and Relvar[®] Ellipta's asthma studies HZA106827 and HZA113091 (GSK Breo Ellipta Advisory Committee briefing document, March 2015) on the treatment effect of the three different doses of active control over placebo. Table 13-4 summarizes the key inclusion criteria for these studies, the adjusted mean for each treatment of active control and placebo, standard error (SE) of the mean, treatment difference, and its 95% CI. In addition the table summarizes the meta-analysis based on the pooled estimates from these studies.

From Table 13-4, the historical evidence of drug effect of active control over placebo (from the meta-analysis) is 354 mL with its 95% CI from 281 mL to 426 mL. Hence based on the lower limit of the pooled estimate, 281 mL, by demonstrating the NI with the chosen NI margin of -90 mL, the treatment effect of QMF149 would be at least 191 mL over (putative) placebo with 95% confidence level, which represents 68% preservation of the treatment effect of active control over placebo.

Table 13-4 Historical evidence of sensitivity of drug effect of active control fixed-dose combination (FDC) for trough FEV₁ in patients with persistent asthma

Study (Duration)	Key Inclusion Criteria	Treatment (n)	Mean (L)* (SE)	Difference vs. placebo (95% CI)
Nathan et. al. (12 weeks)	
 ≥ 12 years old with asthma requiring pharmacotherapy for at least 6 month before the study Use of ICS therapy for ≥ 3 months before the study and at a consistent dose for the previous month 40% < FEV₁ < 85% ≥ 15% increase in FEV₁ from pre to post SABA 	FDC 42/220 µg BID (n = 92)	0.41 (0.04)	0.53 (0.405, 0.655)
		Placebo (n = 87)	-0.12 (0.05)	
Kavura et. al. (12 weeks)	
 ≥ 12 years old with asthma requiring pharmacotherapy for at least 6 month before the study Use of ICS therapy for ≥ 3 months before the study and at a consistent dose for the previous month 40% < FEV₁ < 85% ≥ 15% increase in FEV₁ from pre to post SABA 	FDC 50/100 µg BID (n = 87)	0.51 (0.05)	0.50 (0.319, 0.681)
		Placebo (n = 77)	0.01 (0.07)	
Relvar Asthma Program 2015	See Table 13-5	FDC 50/250 µg BID (n=389)		0.191** (0.089, 0.293)

(Briefing Book)		Placebo (n=193)		
Meta-Analysis***		FDC (n = 576)		0.354 (0.281, 0.426)
		Placebo (n = 357)		

* Change from baseline in pre-dose FEV₁ at week 12.

** Treatment effect is estimated based on combining studies HZA106827 and HZA113091 from Relvar[®] asthma program (briefing book) as summarized in Table 13-5.

*** Meta-analysis is based on pooling of the results from Nathan et al (2006), Kavuru et al (2000), and Relvar's asthma program from studies HZA106827 and HZA113091 and using the inverse variance weighting method.

Table 13-5 Summary of studies HZA106827 and HZA113091 for trough FEV₁ from Relvar[®] asthma program

Study (Duration)	Key Inclusion Criteria	Treatment (n)	Mean (L) (SE)	Treatment Difference (95% CI)
Relvar Asthma Program Study HZA106827 (12 weeks)	
 Outpatients at least 12 years of age Male and female; female subjects of childbearing potential must be willing to use birth control Pre-bronchodilator FEV₁ of 40-90% predicted normal Reversibility FEV₁ of at least 12% and 200 mL Current asthma therapy includes inhaled corticosteroid use for at least 12 weeks prior to first visit 	FF/VI 100/25 µg (n=200)	0.368 (0.0304)	0.172 (0.087, 0.258)
		Placebo (n=193)	0.196 (0.0310)	
Relvar Asthma Program Study HZA113091 (24 weeks)	
 Clinical diagnosis of asthma Reversibility of at least 12% and at least 200 mL within 10-40 minutes following 2-4 inhalations of albuterol FEV₁ of 40-85% predicted normal Currently using inhaled corticosteroid therapy 	FF/VI 100/25 µg (n=397)	0.281 (0.0191)	-0.019 (-0.073, 0.034)
		FP/SAL 250/50 µg BID (n=389)	0.300 (0.0193)	

Reference:

Kavuru MD et al (2000) Salmeterol and fluticasone propionate combined in a new powder inhalation device for the treatment of asthma: A randomized, double-blind, placebo-controlled trial. J Allergy Clin Immunol (2000); 105: 1108-16.

Nathan et al (2006) Efficacy and tolerability of fluticasone propionate/salmeterol administered twice daily via Hydrofluoroalkane 134a metered-dose inhaler in adolescent and adult patients

with persistent asthma: a randomized, double-blind, placebo-controlled, 12-week study. *Clinical Therapeutics* (2006); 28: 73-85.

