The comparison of QMF149 150/320 µg o.d. vs active control (salmeterol xinafoate /fluticasone propionate 50/500 µg b.i.d.) will be performed using the same model as specified for the primary endpoint. The result will be interpreted based on the 95% confidence interval (CI) of the treatment difference of QMF149 – active control. The lower bound of the 95% CI is the difference that can be ruled out. For example, if the lower bound of the 95% CI is larger than the non-inferiority margin -90 mL (i.e. the entire 95% CI is to the right of -90 mL), QMF149 150/320 µg can be considered non-inferior to active control, and if the lower bound of the 95% CI is greater than 0, then QMF149 150/320 µg can be considered superior to active control with regard to trough FEV₁ at Week 26. Note that the comparison versus active control is not part of the confirmatory testing strategy.

The estimation of the non-inferiority margin of -90 mL is provided in [Appendix 12](#).

9.5.1.2 ACQ at Weeks 4, 12 and 52

The ACQ-7 measures asthma symptom control and consists of 7 items: 5 on symptom assessment, 1 on rescue bronchodilator use and 1 on airway calibre (FEV₁ % predicted). Patient recall is 1 week. All 7 questions of the ACQ-7 are equally weighted. Items 1-5 are scored along a 7-point response scale, where 0 = totally controlled and 6 = severely uncontrolled. The 7th item will be scored by the investigator based on the FEV₁ % predicted from the equipment provided by spirometry vendor at the site. The total score is calculated as the mean of all questions.

ACQ-7 at post-baseline visits will be analyzed using the same MMRM model as specified for the primary analysis except that baseline FEV₁ will be replaced with baseline ACQ-7 and all post-baseline visits corresponding to ACQ-7 will be included.

Change from baseline in the ACQ-7 will be also analyzed using the same MMRM model.

The proportion of patients who achieve an improvement of at least 0.5 in ACQ-7 (i.e. decrease of ACQ-7 score of at least 0.5 from baseline) at post-baseline visits will be analyzed using the logistic regression model via the generalized estimating equations (GEE). The model will include terms for treatment, age (12 to 17 or ≥ 18 years), region, visit, and treatment-by-visit interaction as fixed effects with baseline ACQ-7, baseline-by-visit interaction, FEV₁ prior to inhalation and FEV₁ within 15 to 30 min post inhalation of salbutamol/albuterol (components of SABA reversibility) as covariates.

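### Appendix 12's assurance behind the -90 mL margin (at least 191 mL over placebo, 68% preserved) rests on a fixed-effect pool of three estimates that reject a common effect, so no preserved fraction can be stated with 95% confidence

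*Protocol*

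**What the plan says.** QMF149 150/320 µg is compared with salmeterol/fluticasone 50/500 µg b.i.d. on trough FEV₁ at Week 26. Non-inferiority is read from the lower 95% limit against -90 mL (Protocol 9.5.1.1, SAP 2.6.2.1). Protocol 9.5.1.1 says "The estimation of the non-inferiority margin of -90 mL is provided in" Appendix 12, and SAP 2.6.2.1 refers to the same appendix. Both sections place the comparison outside the confirmatory testing strategy.

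Appendix 12 gives three estimates of the control's effect over placebo in Table 13-4 and pools them "using the inverse variance weighting method". The pooled effect "is 354 mL with its 95% CI from 281 mL to 426 mL". From the lower limit it concludes that "the treatment effect of QMF149 would be at least 191 mL over (putative) placebo with 95% confidence level, which represents 68% preservation" of the control's effect.

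The third row is not a direct placebo comparison. Its footnote says "Treatment effect is estimated based on combining studies HZA106827 and HZA113091", which Table 13-5 sets out. Appendix 12 reports no heterogeneity statistic, between-study variance or random-effects analysis.

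**The concern.** The 95% assurance needs a valid lower limit for the control's effect. A fixed-effect interval provides one only if the three studies estimate the same quantity. Table 13-4 suggests at a glance that they do not: the upper limit of row 3 (293 mL) lies below the lower limits of row 1 (405 mL) and row 2 (319 mL).

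The 191 mL / 68% sentence is the only quantitative support for -90 mL in either document. If its lower limit leaves out the between-study spread, a reader of a non-inferior result would take away a guaranteed margin over placebo that the historical data do not give.

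**Working it through.** **Inputs** (Table 13-4; SE = CI width / (2 × 1.96)).

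| Row | Comparison with placebo | Effect, L (95% CI) | SE | 1/SE² |
|---|---|---|---|---|
| 1 | 42/220 µg b.i.d., direct, 12 weeks | 0.530 (0.405, 0.655) | 0.0638 | 245.9 |
| 2 | 50/100 µg b.i.d., direct, 12 weeks | 0.500 (0.319, 0.681) | 0.0923 | 117.3 |
| 3 | 50/250 µg b.i.d., indirect | 0.191 (0.089, 0.293) | 0.0520 | 369.2 |

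Row 3 follows from Table 13-5: 0.172 − (−0.019) = 0.191, with a 95% CI of 0.090 to 0.292 when the two errors are combined.

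**Step 1: reproduce the plan's figure.** The fixed-effect pool is Σ(effect/SE²) / Σ(1/SE²) = 0.354 L. Its SE is 1/√732.3 = 0.0370, so the 95% CI is 0.282 to 0.427. This matches 354 mL (281 to 426) within about 1 mL. Then 281 − 90 = 191 mL and 191/281 = 68%. The arithmetic is right for this model. The documents do not use the term fixed effect; that reading rests on the match, and none of the random-effects estimators below gives 354 (281 to 426).

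**Step 2: test for a common effect.** Q = Σ(effect − 0.354)²/SE² = 7.59 + 2.49 + 9.84 = 19.9 on 2 df, p = 0.00005. I² = (19.92 − 2)/19.92 = 90%.

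**Step 3: locate the heterogeneity.** Rows 1 and 2 pool to 520 mL (417 to 623) with Q = 0.07, p = 0.79. Row 3 lies 329 mL lower (95% CI 184 to 474).

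**Step 4: random effects on the same rows.** Weights are 1/(SE² + τ²). The normal lower limit is the mean − 1.96 × SE. The Hartung-Knapp limit uses t on 2 df (4.303) with a variance based on the observed spread. Under REML, τ = 0.181 L, the mean is 0.401 and the SE is 0.112. The normal limits are 0.401 ± 1.96 × 0.112 = 0.181 to 0.621. The Hartung-Knapp SE is 0.110, so the lower limit is 0.401 − 4.303 × 0.110 = −0.073.

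| Estimator of τ² | Pooled, mL | Lower limit, normal | Minus 90 | Share of lower limit | Lower limit, Hartung-Knapp |
|---|---|---|---|---|---|
| DerSimonian-Laird | 402 | 161 | 71 | 44% | −71 |
| REML | 401 | 181 | 91 | 50% | −73 |
| Paule-Mandel | 400 | 184 | 94 | 51% | −74 |
| Hedges | 400 | 188 | 98 | 52% | −74 |
| Sidik-Jonkman | 400 | 188 | 98 | 52% | −74 |
| Hunter-Schmidt | 399 | 209 | 119 | 57% | −78 |
| ML | 398 | 216 | 126 | 58% | −80 |

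The random-effects means are higher than 354 mL; the loss is in precision. The Q-profile 95% CI for τ runs from about 0.08 to 1.18 L, so three inputs barely determine it.

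**Step 5: combine the errors instead of stacking limits.** Assume SD 380 mL (Protocol 9.8) and 360 completers per arm (Protocol 4). The trial SE is √(2 × 0.38²/360) = 0.0283 L. A result just meeting the margin then has an estimate of −0.090 + 1.96 × 0.0283 = −0.0345 L. With normal limits, the lower limit over placebo is 0.354 − 0.0345 − 1.96 × √(0.0370² + 0.0283²) = 0.229 L for the fixed-effect pool. Under REML it is 0.401 − 0.0345 − 1.96 × √(0.112² + 0.0283²) = 0.139 L.

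**The case against.** Four points can be made for the plan.

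- *The comparison is not confirmatory.* This stands. No primary or key secondary test depends on it, the sample size is driven by the MF comparisons, and the documents set no preservation target that could be failed. It limits the severity but does not make the stated assurance correct.
- *Taking the margin off a lower limit is already conservative.* This is partly right. On the combined-error basis the REML figure is 139 mL, about 50 mL below the stated 191 mL. Like for like, however, the fixed-effect figure on that basis is 229 mL, so a gap of about 90 mL remains.
- *The problem is row 3 rather than the pooling model.* There is force in this. Row 3 is indirect through FF/VI and links a 12-week with a 24-week study. Its source studies also required reversibility of at least 12% and 200 mL, against at least 15% in rows 1 and 2. The choice of inputs moves the answer more than the choice of τ² estimator. Rows 1 and 2 alone would retain 417 − 90 = 327 mL (78%), and row 3 alone 89 − 90 = −1 mL. That is a reason to name row 3 as the source; it does not rescue a pooled interval that treats all three rows as one effect.
- *Three inputs cannot estimate τ.* This is true, and it applies to any replacement figure as well. It does not justify setting τ to zero when the rows reject zero.

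A reader might infer that the correct preservation is 50%, or 91 mL. The table does not support that: 44 to 58% varies only the τ² estimator under normal limits, and Hartung-Knapp limits on the same rows fall below zero. A reader might also infer that -90 mL is invalid or that the comparison must be dropped. Nothing in the documents supports that either.

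**Conclusion.** The concern holds as a point about the stated assurance. The 191 mL / 68% figures are computed correctly from a fixed-effect pool, but the three rows reject that model and Appendix 12 does not say so. The 281 mL lower limit is therefore too high to carry a 95% statement.

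Under random effects with normal limits, the retained effect would be about 91 mL (REML), with 71 to 126 mL across estimators. With Hartung-Knapp limits the lower limit is about −71 to −80 mL before the margin is subtracted. The direction of the error is clear, but its exact size is not: with three inputs, no preserved fraction can be stated with 95% confidence.

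The conclusion assumes that the tabulated intervals are normal-theory intervals. With SEs for rows 1 and 2 taken from the tabulated arm SEs instead, Q is 20.2 and REML retains 93 mL (51%), so it is not sensitive to that choice. The effect is confined to how one secondary comparison is interpreted.

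**What to change.** Change Appendix 12 only.

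1. In Table 13-4, label the pooled row as fixed effect and report Q = 19.9 on 2 df, p < 0.001, I² = 90%.
2. Remove the 191 mL at 95% confidence and the 68% figure as an assurance. State instead that the estimates are heterogeneous. Add that random effects on the same rows (REML, normal-approximation limits) give 401 mL (181 to 621), which would retain about 91 mL or 50% at -90 mL, with 44 to 58% across estimators. Add that Hartung-Knapp limits with three inputs fall below zero (about −71 to −80 mL), so a preserved fraction cannot be stated with 95% confidence.
3. Identify row 3 as the source of the heterogeneity (indirect through FF/VI, linking a 12-week and a 24-week study). Note also that no input used 50/500 µg b.i.d., the control regimen in this trial.

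Keep the -90 mL margin and every analysis. Protocol 9.5.1.1 and SAP 2.6.2.1 need no edit, since both already refer to Appendix 12.

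The cost is a paragraph and a table label, with no new data and no change to model, sample size, power or alpha. The wording has to go through a protocol amendment with the approvals in Protocol 11.1, and the margin's stated support becomes less favourable.
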